14.2 Demographic and Baseline Characteristics

The following demographic variables at screening will be summarized by dose level: race, gender, age, height and weight.

14.3 Analysis of Primary Endpoint

The safety and tolerability data will be summarized by dosing cohort. Adverse events will be tabulated by dosing cohort and will include the number of participants for whom the event occurred, the rate of occurrence, and the severity and relationship to study drug. We may be underpowered to perform Fisher's exact tests to compare crude rates of adverse events between dosing cohorts or to perform adequate Cochran-Armitage trend tests for dose-toxicity.

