4 STUDY DESIGN

4.1 Study Overview

Prior trials evaluating latent reactivating agents have demonstrated that a “priming” period appears to yield greater latency reversal.^{5,7} Therefore, we will perform this multi-center, phase I clinical study of kansui in eight HIV-infected ART-suppressed participants as a dose escalation trial with a double-blinded, randomized, placebo-controlled crossover cohort. The first two participants will complete a kansui-only treatment phase in which they will be given a single, open label 1g dose of *Euphorbia kansui* extract powder prepared as tea. The second group of six participants will complete the study twice (once on a decaffeinated black tea placebo treatment arm and once with the kansui treatment arm) in a randomized, double-blinded, placebo-controlled crossover design. Which treatment arm occurs first will be randomly assigned and will include a 56-day washout period between the two phases. A second screening visit will occur immediately following the washout period on Day 88. The second screening visit will occur 14-days prior to starting the second treatment assignment on Day 102; the second treatment phase will therefore begin on Day 88 and end on Day 101 (See Study Events Table). As indicated by the dose-escalation design of the study, participants in the kansui treatment phase for group 2 will receive 3 consecutive daily 1g doses of *Euphorbia kansui* extract powder served as tea.

We propose using a crossover double-blinded design due to our experience in performing *in vivo* studies of latent HIV reactivation. We have previously demonstrated statistically significant inter-individual differences in baseline values of the virologic and immunologic outcomes proposed in our study.² For these reasons, we have applied a similar crossover study design in another recent study which allowed the ability to detect even small differences in HIV RNA levels after intervention.³⁵ Therefore, due to the small detectable changes that most HIV latent reactivating agents (LRAs) produce at the doses tested in these trials^{2,5,36,37} and the possibility of small detected changes from our trial of *kansui*, a within-subject control component to the study will allow us the greatest ability to accurately detect treatment-related differences in our study outcome measures.³⁸

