Subjects will initiate dosing on separate days. All safety data from each cohort (through week two of observation) will be collated and presented to an SMC before we escalate to the next dose level, as described below. We hypothesize that 1 g of kansui powdered, measured and prepared as tea, given as a single or 3 consecutive daily doses will be safe and well tolerated. We also hypothesize that kansui given as a single or 3 consecutive daily doses may induce T cell activation (CD69, CD38, and/or HLA-DR expression on CD4+ and CD8+ T cells) and latent HIV reactivation (cell-associated HIV RNA and plasma HIV RNA).

Participants will be screened for eligibility. Individuals meeting inclusion criteria without meeting exclusion criteria will be enrolled in the study in sequential dosing cohorts as below. The following treatment regimens will be used:

- Cohort 1: Kansui Phase of (1 g) x 1 dose (the first N = 2 participants)
- Cohort 2: Kansui Phase of (1 g) x 3 consecutive daily doses that is either preceded or followed by a Placebo Phase (the final N = 6 participants)

Study participants will be followed for 31 days following each treatment phase. There will also be a 56-day washout period in between the two treatment phases. The total duration of the study is expected to be up to 45 days for Cohort 1 and up to 146 days for Cohort 2 (See Study Events Table).

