9.2.7 Adverse Events

Information regarding occurrence of adverse events will be captured throughout the study. Duration (start and stop dates and times), severity/grade, outcome, treatment and relation to study drug will be recorded on the case report form (CRF). Criteria for participant management, dose interruptions, modifications, and discontinuation of treatment will be mandated only for toxicities attributable to kansui.

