14.5 Sample Size

A total of 8 participants (2 in dosing cohort 1 and 6 in dosing cohort 2) will contribute to the analysis, with 8 or 25 timepoint measures, respectively. The within-individual variability will be reduced by repeated measurements post-dose. Based on existing data from our study population regarding the percent CD38+HLA-DR+ CD4+ T cells (standard deviation of 4.9%) in our study population and a paired, one sample, repeated measures analysis, we will have greater than 80% power to detect a 2.7% change in CD4+ T cell activation levels post-dose. Similarly, we will have greater than 80% power to detect a 17% change in cell-associated HIV-1 RNA and a 0.37% change in plasma HIV-1 RNA.

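### Section 14.3 tabulates adverse-event rates by dosing cohort with no common window and no kansui/placebo split, so crude rates would tend to be higher in the three-dose cohort even if the tea were inert

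*Combined protocol and SAP*

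**What the plan says.** The synopsis makes safety the primary endpoint, framed as the absence of any clinical or laboratory effect of Grade 2 or above. Section 14.3 gives its analysis: "Adverse events will be tabulated by dosing cohort and will include the number of participants for whom the event occurred, the rate of occurrence", together with severity and relationship to study drug. On testing, the section offers only a caution that the sample may be too small, using Fisher's test, to "compare crude rates of adverse events between dosing cohorts or to perform adequate Cochran-Armitage trend tests for dose-toxicity". It names no denominator, no observation window, no separation of Cohort 2's two phases and no place for events between them.

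Three other provisions bear on this.

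- Collection: Section 9.2.7 says "Information regarding occurrence of adverse events will be captured throughout the study". Section 10.1 counts abnormal laboratory findings as adverse events and has the investigator ask about events at every visit.
- Size and schedule: Section 14.5 says "A total of 8 participants (2 in dosing cohort 1 and 6 in dosing cohort 2) will contribute to the analysis", and it counts 8 timepoints per participant in Cohort 1 and 25 in Cohort 2. Section 4.1 gives time on study as "up to 45 days for Cohort 1 and up to 146 days for Cohort 2".
- Dates: Section 4.1 says "the second treatment phase will therefore begin on Day 88 and end on Day 101", although the same sentence starts the second treatment assignment on Day 102. Section 8.1 also gives Day 102, and Section 9 gives Days 102 to 132.

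**The concern.** A crude rate can be compared between groups only if the groups were watched for similar lengths of time and checked similarly often. Here they were not. Cohort 2 is a crossover, so a table by dosing cohort merges events on kansui, events on placebo and events in the washout into one figure, and sets it beside a single 31-day kansui exposure. Even with placebo and washout removed, three dosing days bring more blood draws and more adverse-event reviews than one.

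Because laboratory abnormalities count, the chance of recording at least one event rises with the number of looks. A reader of the planned table could take a schedule effect for a dose effect on the trial's primary endpoint. The like-for-like contrast that the design provides, kansui against placebo in the same six people, would not appear for adverse events.

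**Working it through.** **Reproducing the plan's own counts.** The Section 9 events tables give 8 timepoints for Cohort 1, and 13 (phase 1) + 12 (phase 2) = 25 for Cohort 2, as Section 14.5 states. The column header for the third dosing day is broken in the extracted text; Section 9.4 confirms sampling at 0, 0.5, 2 and 4 h on Days 3 and 104. Durations also agree: 14 + 31 = 45 and 14 + 132 = 146 days.

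**Checks after first dose, per participant.**

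| | Cohort 1 | Cohort 2, one phase | Cohort 2, pooled |
|---|---|---|---|
| Blood counts | 5 | 10 | 10 + 12 = 22 |
| Metabolic panels | 2 | 4 | 4 + 6 = 10 |
| Adverse-event reviews | 2 | 4 | 4 + 6 = 10 |
| Calendar days | 31 | 31 | 132 |

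Cohort 1's five blood counts are at 0.5, 2 and 4 h on Day 1, Day 2 and Day 31. One Cohort 2 phase adds Day 2 (0 h) and four draws on Day 3, with its 24-hour visit on Day 4. The pooled column also takes in Day 88 and the pre-dose Day 102 visit. The placebo phase has the same post-dose schedule as the kansui phase.

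**Effect for an inert tea.** The documents give no per-draw rate of flagged values, so q is an assumption. P(at least one) = 1 − (1 − q)^n.

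- All draws independent, n = 5 v 10: q = 1%, 4.9% v 9.6%; q = 2%, 10% v 18%; q = 5%, 1 − 0.95^5 = 22.6% v 1 − 0.95^10 = 40.1%.
- Each day one look, n = 3 (Days 1, 2, 31) v 5 (Days 1, 2, 3, 4, 31): q = 5%, 1 − 0.95^3 = 14.3% v 1 − 0.95^5 = 22.6%.
- Values that persist fully within a person: no gap.
- Pooled Cohort 2, independent draws, q = 5%: 1 − 0.95^22 = 67.6%, against 22.6% in Cohort 1.

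**How often the table would mislead.** Exact enumeration over 2 v 6 participants, independent draws and q from 1% to 20%: the three-dose kansui phase has the higher crude proportion in 41% to 66% of trials. With equal checks the figure is 24% to 48%, because the groups are so small and unequal. At an assumed two-sided 0.05, only 0/2 v 6/6 (p = 1/28 = 0.036) or its reverse would be significant by Fisher's test. A false upward result occurs in under 0.1% to 5.4% of trials.

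**After matching.** On shared checks the counts are 5 v 5 blood counts, 2 v 2 panels and 2 v 2 reviews over 31 v 31 days, and the expected ratio for an inert tea is 1.0.

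**The case against.** Several stronger readings are tempting, and the documents do not support them.

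- *Section 14.3 will test crude rates between cohorts.* It will not, as written. The sentence is a caution about power; only the descriptive table is committed.
- *The first treatment is observed for 101 days against 31 for the second.* Days 1-101 and 102-132 are correct as calendar spans, but charging Days 32-101 to the first treatment is a rule the plan never states. The synopsis gives 31 days of follow-up per arm, and the events table has no procedures in the washout. It would in any case be a contrast of periods within Cohort 2, not of doses, and order is randomised. What stands is that events from those days can be recorded at Day 88 or Day 102 and have no stated place in the table.
- *An inert tea would show a dose-toxicity gradient.* It would only tend to look worse at three doses than at one; ties and reversals are common. With placebo entered as dose 0, the expected proportions at q = 5% with independent draws are 40%, 23% and 40% for 0, 1 and 3 doses, which is no gradient.

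Further points in the plan's favour have weight. Same-day draws are correlated, so the independent-draw figures are an upper case. Participants are screened for haemoglobin, and Section 10.1 grades laboratory abnormalities judged clinically significant, so q may be low. Adverse events carry start and stop dates, so Cohort 1's Day 31 review can reach back to Day 2; twice the reviews is not twice the clinical ascertainment. Finally, the move to Cohort 2 is decided by the Safety Monitoring Committee from Cohort 1 data, the stopping rules count drug-related Grade 3 and 4 events, and no stated decision uses the cross-cohort rate.

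These points limit the size and consequence. They do not make the tabulated rates comparable.

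**Conclusion.** The concern holds as a defect in the descriptive safety table. Followed literally, Section 14.3 sets 132 days, 22 blood counts and 10 reviews per Cohort 2 participant, covering kansui, placebo and washout, against 31 days, 5 and 2 in Cohort 1. The kansui phase alone has twice the post-dose checks. These counts come directly from the schedule and need no assumption.

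The resulting distortion does need assumptions. At 5% per look it is 23% v 40% with independent draws and about 14% v 23% with one look per day; it shrinks with lower rates and vanishes if values persist fully. The direction is a tendency, and a false significant result would be rare even if someone ran the test. The harm is a misleading reading of the primary endpoint, which is worth preventing before tables are produced. The date conflict in Section 4.1 is mainly a label, but it has to be settled before any window can be fixed.

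**What to change.** In Section 14.3:

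1. Tabulate adverse events by treatment received: one-dose kansui, three-dose kansui, placebo. Use a common window of Days 1-31 from the first dose of that treatment (Days 1-31 or Days 102-132 on the Section 9 dates).
2. Show kansui beside placebo within Cohort 2 as the like-for-like comparison.
3. Report Days 32-101 in a separate row.
4. For laboratory events, give flagged draws over draws taken.
5. Add a sensitivity comparison of the two cohorts on every check they share: Day 1 at 0.5, 2 and 4 h, 24 h after the last dose, and Day 31.
6. Keep every event in the full listings, so that events after the second and third doses stay visible.

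Reconcile the second-phase dates in Section 4.1 with Sections 8.1 and 9.

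The cost is analysis wording and one or two extra tables, with no added participants, visits or samples. The sensitivity comparison uses fewer draws: 5 of Cohort 2's 10 post-dose blood counts per phase, leaving out those on Days 2 and 3. It should therefore supplement the main table, not replace it.

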14.4 Analysis of Secondary Endpoints

We will perform Wilcoxon rank sum tests to compare levels of immune activation (CD69, CD38, and/or HLA-DR expression on CD4+ and CD8+ T cells) between dosing cohorts and Wilcoxon signed rank tests to compare measures within individuals. We will perform linear mixed effects modeling to compare the effect of *Euphorbia kansui* extract powder prepared as tea on immune activation over time and account for repeated measures within individuals, compared to pre-treatment (using the average of three baseline measures). Similarly, we will perform linear mixed effects regression modeling to assess changes in CA-US RNA levels and use negative binomial mixed effects

modeling to changes in plasma HIV RNA levels, before and after kansui administration (the reference will be the average of three baseline measures).

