14 STATISTICAL METHODS AND CONSIDERATIONS

14.1 Data Sets Analyzed

[name] will be performing the data analysis for the study. Paired analyses using Wilcoxon signed rank tests will be performed to evaluate whether there is a statistically significant change in markers of immune activation (CD69, CD38, and/or HLA-DR) on CD4+ and CD8+ T cells after a 1, 2, or 3 doses of *Euphorbia kansui* extract powder prepared as tea compared to baseline (reference will be the average of the three baseline measures). Multivariate analyses will then be performed to evaluate the association between kansui and measures of immune activation at post-dosing, using linear mixed effects models, which account for within-participant correlation of observations and allows for greater stability in the estimate of the outcome measures within individuals. Similarly, for measures of the HIV reservoir, we will perform linear mixed effects regression to compare CA-US RNA levels before and after kansui and use negative binomial mixed effects regression (a method to analyze over-dispersed count data) to compare plasma HIV RNA levels before and after kansui administration (reference will be the average of three baseline measures).

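### The between-cohort test in 14.4 compares absolute activation levels, with no baseline, phase or timepoint, although 4.1 reports that baseline levels differ significantly between people

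*Combined protocol and SAP*

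**What the plan says.** Section 14.4 plans "Wilcoxon rank sum tests to compare levels of immune activation", specified as "between dosing cohorts and Wilcoxon signed rank tests to compare measures within individuals". For the rank-sum part it gives no reference value, no visit and, for Cohort 2, no statement of whether kansui-phase or placebo-phase samples are used.

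Baseline does appear elsewhere. The mixed model in 14.4 estimates the kansui effect over time "compared to pre-treatment (using the average of three baseline measures"), and 14.1 uses the same reference for its paired tests. Those are before-and-after comparisons within a person. The mixed-model text names no cohort term, so the rank-sum test is the only stated immunologic comparison of one dose with three.

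Section 4.1 justifies the crossover by "statistically significant inter-individual differences in baseline values of the virologic and immunologic outcomes proposed in our study" and concludes that "a within-subject control component to the study will allow us the greatest ability to accurately detect treatment-related differences". Section 14.5 gives the numbers: "A total of 8 participants (2 in dosing cohort 1 and 6 in dosing cohort 2) will contribute to the analysis".

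**The concern.** The two cohorts are different people, enrolled one group after the other and not randomised between cohorts. A difference in their post-dose levels contains any effect of one versus three doses, plus whatever difference in level they brought with them. Section 4.1 treats that second component as important enough to shape the design, but the between-cohort test does nothing to remove it. With only 2 people in one group, chance imbalance is hard to avoid.

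The open wording adds a second problem. Cohort 2 contributes 25 measurements per person across two phases, one of them placebo, so an analyst following 14.4 could choose among many visits and either phase. At stake is whether the displayed cohort difference can be read as a dose contrast at all.

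**Working it through.** **Nearest stated figure.** The plan gives no power or precision for the between-cohort comparison. The closest figure, in 14.5, is more than 80% power for a 2.7% within-person change in CD4+ activation with SD 4.9% and 8 participants. A paired t calculation with SD 4.9 and n = 8 gives 27% (two-sided 5%). Reaching 80% needs an SD of the averaged change of about 2.34. That is a separate matter, and nothing below depends on it.

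**Inputs from the documents.** Group sizes 2 and 6; SD 4.9 points; yardstick 2.7 points (all from 14.5). Pre-dose activation samples, from the Study Events Tables in section 9:
- Cohort 1 and Cohort 2 phase 1: Day -14, Day -7 and Day 1 hour 0, so three.
- Cohort 2 phase 2: Day 88 and Day 102 hour 0, so two.

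The tables reproduce the counts in 14.5: 3 + 5 = 8 for Cohort 1 and 13 + 12 = 25 for Cohort 2.

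**Assumptions.** 14.5 does not say whether 4.9 is the SD of a level or of a change; I take it as the between-person SD of one level. The 2.7 is a within-person effect, borrowed as a yardstick. The within-person correlation ρ is not given, so a range is shown. I use one post-dose value, equal correlation between visits, and a normal difference in means.

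**Levels.** SE = 4.9 × √(1/2 + 1/6) = 4.00. With no dose effect, P(|difference| > 2.7) = 2 × [1 − Φ(2.7/4.00)] = 0.50.

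**Change from the mean of p baselines.** SD = 4.9 × √[(1 − ρ)(1 + 1/p)], and SE = SD × √(1/2 + 1/6).

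| ρ (assumed) | SE, p = 3 | P(>2.7), p = 3 | SE, p = 2 | P(>2.7), p = 2 |
|---|---|---|---|---|
| 0.1 | 4.38 | 54% | 4.65 | 56% |
| 0.25 | 4.00 | 50% | 4.24 | 52% |
| 0.5 | 3.27 | 41% | 3.46 | 44% |
| 0.7 | 2.53 | 29% | 2.68 | 31% |
| 0.8 | 2.07 | 19% | 2.19 | 22% |
| 0.9 | 1.46 | 6% | 1.55 | 8% |

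Only Cohort 2 participants given kansui second have two baselines in that phase, so the real contrast lies between the two halves of the table.

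**Break-even.** Change and level are equally precise when (1 − ρ)(1 + 1/p) = 1. This gives ρ = 0.25 for three baselines and ρ = 1/3 for two.

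**Limit of the test itself.** There are C(8,2) = 28 possible rank allocations, so the smallest two-sided exact p is 2/28 = 0.071 for levels or changes. One-sided it is 1/28 = 0.036. In simulation at that one-sided size, with a true cohort difference of 2.7, power is about 11% on levels. On changes from three baselines it is 11%, 13%, 24% and 39% at ρ = 0.25, 0.5, 0.8 and 0.9.

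**The case against.** The best defence is that the wording is loose. Section 14.5 itself speaks of a change in activation levels, and 14.1 and the rest of 14.4 repeatedly use the mean of three baselines, so a change may be what was meant. The main biological analyses are already within-person. Comparing one dose with three on activation is not an objective in section 3, section 5.1 disclaims a primary efficacy endpoint, and escalation rests on safety review. All of this stands and keeps the importance low. It does not supply the missing definition: followed as written, 14.4 yields a contrast of levels.

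Some stronger readings are tempting but not supported:
- **The cohorts are compared at misaligned times.** A reader might infer this from Day 2 in Cohort 1 and Day 4 or 105 in Cohort 2. The Study Events Tables and section 9 identify these as the 24-hour follow-up after the last dose, so they match. The defect is that 14.4 names no time.
- **The cohort difference must mainly reflect enrolment.** Section 4.1 reports significance, not size, and no correlation is given. The size of any dose effect is also unknown.
- **The test is invalid.** Under no difference between cohorts, the simulated one-sided size stays at about 0.036 on levels. The cost is precision and exposure to baseline imbalance.
- **Three baselines exist for every kansui phase.** Phase 2 has two.

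**Conclusion.** The point holds as a low-severity defect in the quantity compared, confined to the between-cohort rank-sum test. The plan's own statement about baseline variation makes a contrast of raw levels between 2 and 6 non-randomised people hard to interpret, and the observed difference may largely reflect who was enrolled.

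The 50% on levels, against 50% down to 6% on change, is illustrative only. It rests on 4.9 being the SD of a level, on a borrowed yardstick, and on assumed correlations from 0.25 to 0.9. Change is the better quantity when the within-person correlation exceeds 0.25 to 0.33; section 4.1 makes that plausible but does not quantify it. Using change rescues neither significance testing nor the lack of randomisation, so the comparison is descriptive either way.

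**What to change.** In 14.4, define the between-cohort quantity as each person's change from the mean of the pre-dose values of their kansui phase. Take it at two named visits: 24 hours after the last kansui dose, and the Day 31 or Day 132 visit of that phase. State that placebo-phase samples are not used for this contrast. Report it descriptively with individual values by cohort, without a significance claim.

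Say explicitly that the baseline is a mean of three values for phase 1 and two for phase 2. Also reconcile section 9.1.2, whose Day -7 blood list omits immunophenotyping, with the Study Events Tables, which mark it.

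The cost is a few sentences, with no added visits, samples or participants beyond the Study Events Tables. The downside is a slightly noisier contrast than levels if the within-person correlation is below the break-even.
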